10.5. Appendix 5: Genetics

Use/Analysis of DNA

- Genetic variation may impact a patient's response to study drug, susceptibility to, and severity and progression of disease. Variable response to study drug may be due to genetic determinants that impact drug absorption, distribution, metabolism, and excretion; mechanism of action of the drug; disease etiology; and/or molecular subtype of the disease being treated. Therefore, where local regulations and IRB/IEC allow, a blood sample will be collected for DNA analysis from consenting patients.
- DNA samples will be used for research related to ALXN1840 or WD and related diseases. They may also be used to develop tests/assays including diagnostic tests related to ALXN1840 and WD. Genetic research may consist of the analysis of one or more candidate genes or the analysis of genetic markers throughout the genome or analysis of the entire genome (as appropriate).
- DNA samples will be analyzed for variants in the coding and regulatory sequences of the *ATP7B* gene.
- Additional unspecified analyses may be conducted in the future if it is hypothesized that this may help resolve issues with the clinical data.
- The samples may be analyzed as part of a multi-study assessment of genetic factors involved in the response to ALXN1840 or study drugs of this class to understand study disease or related conditions.
- The results of genetic analyses may be reported in the clinical study report or in a separate study summary.
- Alexion will store the DNA samples in a secure storage space with adequate measures to protect confidentiality.
- The DNA samples will be retained while research on ALXN1840 continues but no longer than 15 years or other period as per local requirements.

10.6. Appendix 6: Abbreviations

Abbreviation	Definition
AASLD	American Association for the Study of Liver Diseases
AE	Adverse event
ALT	Alanine aminotransferase
ANCOVA	Analysis of covariance
AST	Aspartate transaminase
AUEC	Area under the effect-time curve
BMI	Body mass index
BPRS	Brief Psychiatric Rating Scale-24;
CGI	Clinical Global Impression
CGI-I	Clinical Global Impression-Improvement Scale
CGI-S	Clinical Global Impression-Severity Scale
CIOMS	Council for International Organizations of Medical Sciences
CKD	Chronic kidney disease
CLDQ	Chronic liver disease questionnaire
cNCC	Calculated non-ceruloplasmin-bound Cu
CONSORT	Consolidated Standards of Reporting Trials
Cp	Ceruloplasmin
CpC	Ceruloplasmin bound Cu
CRF	Case report form
Cu	Copper
CYP	Cytochrome P450
DMC	Data Monitoring Committee
dNCC	Directly measure non-ceruloplasmin bound Cu
EASL	European Association for the Study of the Liver
EDC	Electronic data capture
EOS	End of Study
EQ-5D	EuroQoL 5 Dimensions
EQ VAS	EuroQol visual analog scale
ET	Early Termination
FDA	Food and Drug Administration
FSH	Follicle-stimulating hormone
GDS	Global Drug Safety
HIPAA	Health Insurance Portability and Accountability Act
IB	Investigator's Brochure
ICF	Informed consent form
IEC	Institutional Ethics Committee
INR	International normalized ratio for prothrombin time

Abbreviation	Definition
IRB	Institutional Review Board
LLT	Lowest level term
LS	Least-squares
MedDRA	Medical Dictionary for Regulatory Activities
MELD	Model for End-Stage Liver Disease
MMRM	Mixed model repeated measures
Mo	Molybdenum
MR(E)	Magnetic resonance (elastography)
MRI	Magnetic resonance imaging
MT	Metallothionein
NCC	Non-ceruloplasmin-bound Cu
NIMP	Non-investigational medicinal product
PD	Pharmacodynamic(s)
PDFF	Proton density fat fraction
PK	Pharmacokinetic(s)
PT-INR	Prothrombin time-international normalized ratio
PUF	Plasma ultrafiltrate
QOD	Once every other day
QD	Once a day
SAE	Serious adverse event
SoA	Schedule of Activities
SoC	Standard of care
SUSAR	Suspected unexpected serious adverse reaction
TSQM-9	Treatment Satisfaction Questionnaire for Medication-9
ULN	Upper limit of normal
UNS	Unscheduled
UWDRS	Unified Wilson Disease Rating Scale
WD	Wilson disease
WOCBP	Woman of childbearing potential

10.7. Appendix 7: Protocol Amendment History

The Protocol Amendment Summary of Changes Table for the current amendment is located directly before the Table of Contents (TOC).

Original Protocol	20 Dec 2019
Amendment 1 (Austria)	07 May 2020
Amendment 2 (Germany)	03 Aug 2020
Amendment 3 (Denmark)	10 Aug 2020
Amendment 4 (United Kingdom)	23 April 2021

Amendment 1 (07 May 2020)

This amendment is considered to be substantial based on the criteria set forth in Article 10(a) of Directive 2001/20/EC of the European Parliament and the Council of the European Union.

Overall Rationale for the Amendment

This amendment was prepared to add information on monthly pregnancy testing for female patients of childbearing potential who are enrolled in an interventional clinical study. This is a legal requirement in Austria, according to Article 30 of the Austrian Drug Law. This amendment applies only to Austria.

Changes to the Protocol

Section # and Name	Description of Change	Brief Rationale and/or Clarifications
Section 1.2 Schedule of Activities, Tables 1 and 2 Section 5.1, Inclusion Criteria Section 10.4 Appendix 4: Pregnancy Information	Addition of requirement for female subjects of childbearing potential to perform monthly pregnancy testing at their home throughout the study	It is a legal requirement in Austria to include monthly pregnancy tests in clinical studies
Figure 1	Figure corrected to remove mention of treatment-naïve patients	Treatment-naïve patients are not included in the study.
All sections	Minor editorial updates and corrections	For clarification, and to ensure accuracy and consistency throughout the protocol

Amendment 2 (03 Aug 2020)

This amendment is considered to be substantial based on the criteria set forth in Article 10(a) of Directive 2001/20/EC of the European Parliament and the Council of the European Union.

Overall Rationale for the Amendment

This amendment was prepared to update exclusion criterion relating to clinical study experience and to add information on prohibited concomitant medication in response to a request by the Federal Institute for Drugs and Medical Devices in Germany (BfArM). Additional changes are included in the table below. This amendment only applies to Germany.

Changes to the Protocol

Section # and Name	Description of Change	Brief Rationale and/or Clarifications
Section 5.2, Exclusion Criteria	Prior clinical study experience limited to 3 months (or 5 half-lives of the administered investigational medicinal product, whichever is longer) prior to study start.	More detailed language regarding exclusion of patients who participated in any interventional study prior to initiation of Study ALXN1840-WD-205.
Section 6.5, Concomitant Therapy	Standard of care treatment for Wilson disease added as prohibited medication during the treatment period.	Standard of care treatment for Wilson disease and ALXN1840 should not be administered concomitantly.
Figure 1	Figure corrected to remove mention of treatment-naïve patients	Treatment-naïve patients are not included in the study.
All sections	Minor editorial updates and corrections	For clarification, and to ensure accuracy and consistency throughout the protocol

Amendment 3 (10 Aug 2020)

This amendment is considered to be substantial based on the criteria set forth in Article 10(a) of Directive 2001/20/EC of the European Parliament and the Council of the European Union.

Overall Rationale for the Amendment

This amendment was prepared to add information on pregnancy testing for female patients of childbearing potential who are enrolled in an interventional clinical study in response to a request from the Danish Health Authority. Additional minor editorial updates were made for clarification and consistency. This amendment only applies to Denmark.

Changes to the Protocol

Section # and Name	Description of Change	Brief Rationale and/or Clarifications
Section 1.2, Schema, Figure 1	Figure corrected to remove mention of treatment-naïve patients	Treatment-naïve patients are not included in the study.
Section 1.1, Synopsis Section 1.3, Table 1, and Table 2 Section 4.1, Overall Design	Monthly pregnancy testing will be performed for 90 days after the last dose of ALXN1840.	Monthly pregnancy testing, according to the Clinical Trial Facilitation Group (CTFG) guideline on contraception in clinical trials, has been extended based on relevant exposure of ALXN1840.
Section 10.4, Appendix 4, Pregnancy Information	Contraception guidance updated to include duration of use and type.	To further define contraception requirements

All sections	Minor editorial updates and corrections	For clarification, and to ensure accuracy and consistency throughout the protocol
--------------	---	---

Amendment 4 (23 April 2021)

This amendment is considered to be nonsubstantial based on the criteria set forth in Article 10(a) of Directive 2001/20/EC of the European Parliament and the Council of the European Union.

Overall Rationale for the Amendment

The main reason for preparation of this amendment was to add information regarding the coronavirus disease 2019 (COVID-19) vaccine risk assessment, as requested by the UK Medicines and Healthcare products Regulatory Agency (MHRA) in its updated guidance on managing clinical trials during the COVID-19 pandemic. This amendment only applies to the United Kingdom.

Changes to the Protocol

Section # and Name	Description of Change	Brief rationale and/or clarifications
Section 2.3.1.1, Coronavirus Disease 2019; Section 10.6 Appendix 6: COVID-19 Vaccine Risk Assessment	Text on the COVID-19 vaccine risk assessment performed with respect to ALXN1840 added.	To comply with the request by the MHRA for studies performed in the UK.
All sections	Minor editorial updates and corrections	For clarification, and to ensure accuracy and consistency throughout the protocol

Abbreviations: COVID-19 = coronavirus disease 2019; MHRA = Medicines and Healthcare products Regulatory Agency; UK =United Kingdom.

3. LIST OF ABBREVIATIONS AND DEFINITIONS OF TERMS

The following abbreviations and acronyms are used in this Statistical Analysis Plan (SAP).

Table 1: Abbreviations and Acronyms

Abbreviation or Acronym	Explanation
ADL	activities of daily living
AE	adverse event
ALT	alanine aminotransferase
ALP	alkaline phosphatase
AST	aspartate transaminase
ATC	Anatomic Therapeutic Chemical
AUC	area under the plasma concentration versus time curve
AUC _t	area under the plasma concentration versus time curve from time 0 to the last quantifiable concentration
AUC _τ	area under the plasma concentration versus time curve over the dosing interval
AUEC	area under the effect versus time curve
AUEC _{0-48w}	daily mean area under the effect versus time curve of dNCC from 0 to 48 weeks
AUEC _t	area under the effect versus time curve from time 0 to the last quantifiable concentration time
BLQ	below the limit of quantification
BMI	body mass index
BPRS-24	Brief Psychiatric Rating Scale-24
CGI-I	Clinical Global Impression-Improvement Scale
CGI-S	Clinical Global Impression-Severity Scale
CI	confidence interval
CLDQ	Chronic Liver Disease Questionnaire
C _{max}	maximum observed concentration
cNCC	calculated non-ceruloplasmin-bound Cu
Cp	ceruloplasmin
CpC	ceruloplasmin-bound Cu
CRF	case report form
CS	clinically significant
CTCAE	Common Terminology Criteria for Adverse Events

Table 1: Abbreviations and Acronyms

Abbreviation or Acronym	Explanation
C _{trough}	trough (pre-dose) concentration observed at the start of the dosing interval
CV	coefficient of variation
dNCC	directly measured non-ceruloplasmin-bound Cu
ECG	electrocardiogram
eDISH	evaluation of drug-induced serious hepatotoxicity
E _{max}	maximum observed PD concentration in plasma
EoS	End of Study
EQ-5D	EuroQoL 5 Dimensions
EQ-5D-5L	EuroQoL 5 Dimensions 5 Levels
ET	Early Termination
FA	Full Analysis
FIB-4	Fibrosis-4
FSH	follicle-stimulating hormone
GGT	gamma-glutamyl transferase
GM	geometric mean
INR	international normalized ratio
LBC	labile-bound Cu
LLOQ	lower limit of quantification
ln	natural logarithm
LSM	least-squares mean
MedDRA	Medical Dictionary for Regulatory Activities
MELD	Model for End-Stage Liver Disease
MRE	magnetic resonance elastography
MR-PDF	magnetic resonance-proton density fat fraction
NAFLD	nonalcoholic fatty liver disease
NAS	nonalcoholic fatty liver disease activity score
NCC	non-ceruloplasmin-bound Cu
NCI	National Cancer Institute
NCS	not clinically significant
PD	pharmacodynamic(s)

Table 1: Abbreviations and Acronyms

Abbreviation or Acronym	Explanation
PK	pharmacokinetic(s)
PP	Per Protocol
PT	Preferred Term
PTAE	pretreatment adverse event
PUF	plasma ultrafiltrate
QT	interval between the start of the Q wave and the end of the T wave in an ECG
QTcF	QT interval corrected using Fridericia's formula
REML	restricted maximum likelihood
SAE	serious adverse event
SAP	statistical analysis plan
SAS®	Statistical Analysis Software
SoA	schedule of activities
SOC	System Organ Class (MedDRA)
SoC	standard of care
SF-36	Short Form-36
TEAE	treatment-emergent adverse event
TPC	tripartite complex
TSQM-9	Treatment Satisfaction Questionnaire for Medication-9
ULOQ	upper limit of quantification
ULN	upper limit of normal
UWDRS	Unified Wilson Disease Rating Scale
VAS	visual analog scale
WBC	white blood cell
WD	Wilson disease
WHO	World Health Organization

4. DESCRIPTION OF THE PROTOCOL

This is a Phase 2, single-arm, pathologist-blinded study, using liver biopsy specimens to assess copper (Cu) concentration and histopathologic changes in patients with Wilson disease (WD), who are treated with ALXN1840 for 48 weeks followed by an Extension Treatment Period with ALXN1840 for up to an additional 48 weeks. This study is being conducted to evaluate the change from Baseline in liver Cu concentration at 48 weeks in adult patients with WD treated with ALXN1840 at doses up to 30 mg who have been treated for at least 1 year with standard of care (SoC; trientine, penicillamine, and zinc). Currently available SoC medications (e.g., trientine, penicillamine, and zinc) control excess free Cu in the blood but have never been demonstrated prospectively to reduce Cu burden in the human liver.

Approximately 28 patients with WD who are aged 18 years and older will be enrolled into the study globally, such that approximately 24 evaluable patients complete the 48-week Treatment Period.

The planned study duration is approximately 100 weeks, including an up to 4-week Screening Period. A liver biopsy will be performed during the Screening Period up to 4 weeks before the first dose of study drug, followed by a 48-week Treatment Period, which starts on the day of the first dose of study drug. Patients who complete the 48-week Treatment Period will be offered the opportunity to participate in a 48-week Extension Period to evaluate the long-term safety and efficacy of ALXN1840. For patients who enter the Extension Period, Week 48 Visit is the end of the Treatment Period and the beginning of the Extension Period (i.e., the Week 48 Visit and the Extension Period Day 1 visit will occur on the same day). For patients who enter the Extension Period, all assessments for the Week 48 Visit and the liver biopsy must be performed before the first dose of ALXN1840 on Day 1 of the Extension Period. Dosing of ALXN1840 on Extension Period Day 1 marks the beginning of the Extension Period. Patients who do not enter the Extension Period will discontinue dosing at Week 48 following the second liver biopsy and will have a final study visit for safety follow up at Week 52 of the Treatment Period. The schedule of activities is available in Section 9.1. All biopsy specimens will be reviewed and scored by an independent expert hepatopathologist who is blinded to patient identity and biopsy order. The protocol can be referenced for additional details.

The analysis and statistical reporting will be conducted using SAS[®] version 9.4 or higher (SAS Institute Inc., Cary, North Carolina).

4.1. Changes From Analyses Specified in the Protocol

The following changes were made from analyses specified in the Protocol Amendment (approval dated 27 May 2022):

For exploratory endpoints measured only at Baseline and Week 48, a paired sample t-test or a Wilcoxon Signed-rank test will be used to assess Baseline and Week 48 results for continuous or ordinal outcomes, respectively, in this SAP per Section 7.2.4.

These analyses are to replace the ANCOVA or nonparametric ANCOVA models mentioned in Protocol Amendment 5 (approval date 27 May 2023) Section 9.4.1.1 for these endpoints.

4.2. Changes From Analyses Specified in the Previous Version of the Statistical Analysis Plan

The following updates have been made to the SAP version 1.0 approved on 16 Dec 2022:

Section No. and Name	Description of Change	Justifications
Section 3. Table 1. List of Abbreviations and Definitions of Terms	Added the following abbreviations: 
 • cNCC for calculated non-ceruloplasmin-bound Cu • dNCC for directly measured non-ceruloplasmin-bound Cu • AUEC_{0-48W} for daily mean AUEC of dNCC from 0 to 48 weeks • FIB-4 for Fibrosis-4 • PT for Preferred Term • ULOQ for upper limit of quantification 	To align with Protocol Amendment 5
Section 4. Description of the Protocol	Clarified that a liver biopsy is needed for patients entering Extension Period on Week 48 Clarified that all biopsy samples will be reviewed and scored by an independent expert hepatopathologist blinded to identity and biopsy order	To align with Protocol Amendment 5
Section 4.1. Changes From Analyses Specified in the Protocol	Added statements that ANCOVA or nonparametric ANCOVA models are replaced with a paired sample t-test or a Wilcoxon signed-rank test for continuous exploratory endpoints or ordinal exploratory endpoints tested only at Baseline and Week 48	To align with executed analysis and learnings for this study
Section 4.2. Changes From Analyses Specified in the Previous Version of the Statistical Analysis Plan	Provided summary of changes made in this SAP relative to SAP version 1.0 (approval date 16 Dec 2022)	Good documentation practice
Section 5.1.3. The Exploratory Efficacy Endpoints	Added the following exploratory endpoints: 
 • Absolute and percent change in directly measured non-ceruloplasmin-bound Cu (dNCC) and labile-bound Cu (LBC) from Baseline to Week 48 • Daily mean AUEC of dNCC from 0 to 48 weeks 	To align with Protocol Amendment 5

Section No. and Name	Description of Change	Justifications
	Corrected NCC to cNCC Aligned text of MR-PDF with protocol by replacing steatosis with liver stiffness	
Section 5.1.3.10. Fibrosis-4 Index	Newly added section to define Fibrosis-4 (FIB-4)	To align with executed analysis and learnings for this study
Section 5.2.1. Adverse Events	Updated protocol approval date from 20 Dec 2019 to 27 May 2022	To align with Protocol Amendment 5
Section 5.3. Pharmacokinetics/Pharmacodynamics	Added PD endpoints of plasma concentration of directly measured non-ceruloplasmin-bound Cu (dNCC), LBC, and AUEC of dNCC Corrected NCC to cNCC	To align with Protocol Amendment 5
Section 5.4. Biomarkers	Clarified that it is 24-hour urine samples to be collected per the SoA	Administrative updates
Section 6.2. Data Sets in the Treatment Period Section 6.3. Data Sets in the Extension Period	Added “evaluable” after “liver Cu value”	Clarification
Section 6.2. Data Sets in the Treatment Period Section 6.3. Data Sets in the Extension Period	Added “evaluable” after “liver Cu value”	Clarification
Section 7.1.3. Demographics, Disease Characteristics, and History	Removed statement of “Demographic and Baseline disease characteristics will also be produced for the subgroups mentioned in Section 7.2.1.2”	Subgroup analysis is considered unnecessary.
Section 7.1.3.1. Demographics	Added the following demographic variables: 
 • Time since WD diagnosis (months) • Cumulative duration of prior WD treatment (months) • Prior WD therapy • Cirrhosis 	To align with executed analysis and learnings for this study

Section No. and Name	Description of Change	Justifications
Section 7.1.3.2. Disease Characteristics	Added the following disease characteristics variables: 
 • Liver ultrasound • dNCC (µmol/L) • Creatinine (µmol/L) • High-density lipids (mmol/L) • Low-density lipids (mmol/L) • Triglycerides (mmol/L) • 24-hour urinary creatinine (µmol/day) Corrected the following disease characteristics variables: 
 • NCC to cNCC • 24-hour urinary Cu and Mo unit to “ug/day” from “ug/mL” 	To align with Protocol Amendment 5 To align with executed analysis and learnings for this study
Section 7.2.1.1. Handling of Dropouts or Missing Data	Added following note: Liver Cu concentrations reported as < LLOQ or > ULOQ will be considered non-evaluable. Non-evaluable data will be excluded when deriving summary statistics in both liver Cu primary analysis and Cu sensitivity analysis. This same principle will also be applied to the analysis of other live metals	Clarifications
Section 7.2.1.2. Subgroup Analyses	Updated subgroup analyses are considered unnecessary	To align with Protocol Amendment 5
Section 7.2.1.5. Sensitivity Analyses	Clarified to use observation data from patients where both Baseline and Week 48 data are available	To add specifics for sensitivity analysis using observed data
Section 7.2.4. Other Efficacy Analyses	Corrected NCC to cNCC Added dNCC and LBC Added liver metals from liver biopsy specimen for a paired sample t-test at Baseline and Week 48 when applicable	To align with Protocol Amendment 5

Section No. and Name	Description of Change	Justifications
Section 7.2.4. Other Efficacy Analyses	Added FIB-4	To align with executed analysis and learnings for this study
Section 7.2.5.1. Pharmacokinetic and Pharmacodynamic Sampling	Corrected NCC to cNCC Added dNCC and LBC	To align with Protocol Amendment 5
Section 7.2.8. Pharmacodynamic and Biomarker Concentration Analyses	Corrected NCC to cNCC Added dNCC Defined dNCC, AUEC of dNCC, daily mean AUEC of dNCC from 0 to Week 48 (AUEC _{0-48W}), and corresponding analysis plans	To align with Protocol Amendment 5
Section 7.3.3.2 eDISH	Removed “each treatment arm (1840 and SoC) separately” Corrected “eDISH Plot by Treatment Arm” to “eDISH plot for all patients”	Correction. All patients received 1840
Section 7.5. Interim Analyses	Clarified that interim analyses may include safety data only or safety and efficacy data together Clarified that interim analysis outputs may include a full or a subset of listed outputs when appropriate	To align with executed analysis and learnings for this study
Section 9.1 Protocol Schedule of Events	Removed schedule of assessment table and provide reference to Protocol Amendment 5 Section 1.3 Table 1 and Table 2	To align with Protocol Amendment 5
Section 9.4.12 CLDQ	Added specifics regarding CLDQ scoring principles	To clarify how CLDQ scores are derived
All Sections	Replaced copper with Cu and molybdenum with Mo throughout the text when applicable Formatting updates per style guide Spelling and grammar updates	Administrative updates

5. DEFINITIONS

5.1. Efficacy

5.1.1. Primary Endpoint(s)

The primary efficacy endpoint is the change from Baseline to Week 48 in liver Cu concentration.

5.1.2. Secondary Endpoints

The secondary efficacy endpoints are as follows:

- Change from Baseline to Week 48 in steatosis, inflammation, and fibrosis
- Change from Baseline in Clinical Global Impression-Severity Scale (CGI-S)
- Change from Baseline in Clinical Global Impression-Improvement Scale (CGI-I)

5.1.2.1. Steatosis, Inflammation, and Fibrosis

Assessments will be based, in part, on a histological scoring system for nonalcoholic fatty liver disease (NAFLD).

Inflammation will be quantified by the NAFLD activity score (NAS). The score is defined as the unweighted sum of the scores for steatosis (0 to 3), lobular inflammation (0 to 3), and hepatocellular ballooning (0 to 2), thus ranging from 0 to 8 ([Kleiner, 2005](#)).

Steatosis from histology will be evaluated in 2 ways: the steatosis component of the NAS, expressed as an ordinal score ranging from 0 to 3, and morphometric quantification of hepatic fat, expressed as a percentage ([Jayakumar, 2018](#)).

Fibrosis from histology will be evaluated in 2 ways: graded on an ordinal scale from 0 to 4 ([METAVIR, 1994](#)) and by morphometric quantification of hepatic collagen content and alpha-smooth muscle actin (a-SMA), expressed as percentages.

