7. STATISTICAL ANALYSIS

The Treatment Period and Extension Period will be analyzed separately and sequentially. When summarizing by descriptive statistics, continuous variables will be summarized using the number of non-missing values, mean, standard deviation (SD), median, minimum, and maximum. Certain continuous variables may also include 95% confidence intervals (CIs), and certain categorical variables will be summarized as proportions with 95% CIs. Categorical variables will be summarized using percentages and frequency counts. Patient level listings will be provided accordingly without separating the Treatment Period and Extension Period.

Baseline for all assessments will be defined as the last assessment yielding non-missing valid values taken prior to the first dose of ALXN1840. Details can be found in [Appendix 9.4](#).

The analysis and statistical reporting will be conducted using SAS[®] version 9.4 or higher (SAS Institute Inc., Cary, North Carolina).

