7.2.2. Secondary Analyses

All secondary analyses will be performed using the FA Set in the Treatment Period.

Histologic assessments (steatosis, inflammation, and fibrosis) and CGI-S will be summarized for Baseline Visit and post-baseline visits using descriptive statistics. Change from Baseline will also be summarized for each post-baseline visits. Since CGI-I is only collected post-dose, only post-baseline visits will be summarized. In addition, the following analysis will be done.

The CGI-S data will be analyzed using MMRM. In the MMRM model, the response variables will be change from Baseline. Visit and Baseline values will be used as covariates. The restricted maximum likelihood (REML) estimation will be used. An unstructured covariance matrix will be used to model the within-subject error and the Kenward-Roger approximation will be used to estimate the degrees of freedom. If the fit of the unstructured covariance structure fails to converge or a positive definite Hessian matrix is not produced, the following covariance structures will be tried in order until convergence is reached: Toeplitz with heterogeneity, autoregressive with heterogeneity, Toeplitz, autoregressive, and compound symmetry. Based on the model, the comparison of post-baseline versus Baseline time points will be tested using a 2-sided test at the $\alpha = 0.05$ level of significance. The least squares mean (LSM) change from Baseline and associated SE will also be presented along with the 95% CI. The reference SAS code for the MMRM model can be found in Section 9.5.

Mean and 95% CI of CGI-S will be plotted over time. Additionally, patient level data over time will be plotted by spaghetti plot.

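### SAP 5.1.2.1 measures inflammation only by total NAS, so it can fall through fat or ballooning alone, and no planned summary separates lobular inflammation from ballooning

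*SAP*

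**What the plan says.** SAP 5.1.2 lists the secondary histology endpoint as "Change from Baseline to Week 48 in steatosis, inflammation, and fibrosis", that is, three separate concepts.

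SAP 5.1.2.1 then assigns the measures:

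- **Inflammation** has one: "Inflammation will be quantified by the NAFLD activity score (NAS". NAS is defined there as the "unweighted sum of the scores for steatosis (0 to 3), lobular inflammation (0 to 3), and hepatocellular ballooning" (0 to 2), with a total range of 0 to 8.
- **Steatosis** has two: "the steatosis component of the NAS, expressed as an ordinal score ranging from 0 to 3", and a morphometric fat percentage.
- **Fibrosis** also has two: the METAVIR stage (0 to 4), and morphometry of collagen and alpha-smooth muscle actin.

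For reporting, SAP 7.2.2 states: "Histologic assessments (steatosis, inflammation, and fibrosis) and CGI-S will be summarized for Baseline Visit and post-baseline visits using descriptive statistics". It adds: "Change from Baseline will also be summarized for each post-baseline visits". Under SAP 7, "continuous variables will be summarized using the number of non-missing values, mean, standard deviation (SD), median, minimum, and maximum". Neither section names a summary of the lobular inflammation or ballooning component. SAP 7 also says: "Patient level listings will be provided accordingly without separating the Treatment Period and Extension Period".

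Protocol 8.1.1 calls for METAVIR scoring of both disease activity and fibrosis and does not mention NAS. The SAP uses METAVIR for fibrosis only. SAP 4.1 lists one change from the protocol's analyses, the replacement of the ANCOVA models for certain exploratory endpoints.

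**The concern.** The quantity reported as inflammation is a composite in which most of the available points are something else. Its steatosis part is the same 0–3 score that the same section reports under steatosis, so one change in fat counts under two of the three named concepts. Followed as written, the plan can report a fall in inflammation when lobular inflammation is unchanged or worse.

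Protocol 4.2 gives the drug's effect on inflammation and tissue injury in the liver as a reason for doing the histology. A reader of the planned summaries could not say which of the two had changed. The one other activity score the protocol requires, METAVIR activity, has no place in the planned summaries either.

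The stake is interpretation of a secondary, descriptive result. The primary copper analysis, its test and the sample size are untouched.

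**Working it through.** **Inputs** (all from SAP 5.1.2.1): steatosis S = 0–3, lobular inflammation L = 0–3, ballooning B = 0–2, and NAS = S + L + B.

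**1. Reproduce the stated range.** The minimum is 0 and the maximum is 3 + 3 + 2 = 8, as the SAP says. Lobular inflammation supplies at most 3/8 = 37.5% of the points; steatosis and ballooning together supply 5/8 = 62.5%.

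**2. Falls in NAS with L unchanged.** NAS can fall by up to 3 through S alone, 2 through B alone, and 5 through both.

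**3. All possible patterns.** There are 4 × 4 × 3 = 48 score states and 48 × 48 = 2304 baseline-to-Week-48 pairs. NAS falls in 975 of them. In 232 of those L is unchanged and in 134 it is worse, so 232 + 134 = 366 falls (366/975 = 37.5%) occur without a lobular fall.

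**4. Use the separate steatosis summary.** The mean of (ΔNAS − ΔS) equals mean ΔNAS minus mean ΔS when both are taken over the same biopsies. A purely fat-driven fall therefore shows up as a zero remainder. The remainder is R = L + B, range 0–5.

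**5. What the remainder leaves open.** Within one patient ΔL = ΔR − ΔB, with ΔB between −2 and +2 and ΔL between −3 and +3:

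| Change in L + B | Possible change in L |
|---|---|
| 0 | −2 to +2 |
| −1 | −3 to +1 |
| −2 | −3 to 0 |
| −3 | −3 to −1 |
| −4 | −3 to −2 |
| −5 | −3 |

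Only a remainder fall of 3 or more guarantees a lobular fall. Of the 12 × 12 = 144 lobular–ballooning pairs, R falls in 58. In 12 of these L is unchanged and in 3 it is worse, 15 in all.

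**6. Subtraction does not work for medians.** Take three patients with ballooning unchanged and changes in (S, L) of (−1, 0), (0, +1) and (−2, +1).

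- Their NAS changes are −1, +1 and −1.
- Medians: −1 for NAS minus −1 for steatosis gives 0, yet the median lobular change is +1.
- Means: −1/3 − (−1) = +2/3, which is the mean lobular change.

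The counts in steps 3 and 5 are numbers of possible score patterns. They are not expected frequencies, because the documents give no baseline histology distribution.

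**The case against.** The strongest reply is that little is really hidden. Steatosis is reported in its own right, by ordinal score and by morphometry, so a fat-driven fall in NAS can be recognised. NAS and its steatosis component come from the same reading, so their n should normally match. This stands, and it narrows the gap to lobular inflammation versus ballooning.

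Second, protocol 4.2 speaks of tissue injury as well as inflammation, and ballooning can reasonably be read as injury. The remainder would then track that broader purpose. But the endpoint in SAP 5.1.2 is inflammation, and the remainder cannot show which of the two moved.

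Third, protocol 9.4 promises patient-level listings of every variable, and with about 24 evaluable patients a listing can be tabulated by hand. That is true if the components are listed. The SAP does not say they will be, and a listing is not a summary.

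Fourth, SAP 5.1.2.1 says the NAFLD system is used only in part, and table shells that might show the components are not among the documents. The final row labels are therefore unknown, but no other inflammation measure is named.

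On METAVIR, SAP 4.1 covers changes to analyses, and protocol 9.4.1.1 names no analysis of METAVIR activity, so a formal duty to declare its omission is arguable. It remains a score that the protocol requires and the SAP does not name in any summary.

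Finally, SAP 4.2 attributes several revisions to analyses already executed, so renaming a measure now could look data-driven. Keeping the prespecified NAS summary in full, adding only descriptive rows and recording the change answers most of that.

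**Conclusion.** The concern holds. By the SAP's own definition, the only inflammation measure draws up to 5 of its 8 points from steatosis and ballooning. No planned summary isolates lobular inflammation, and METAVIR activity is required by the protocol but has no named summary in the SAP.

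Subtracting mean steatosis change removes the fat part, provided that means are reported and the same biopsies contribute to both. What then remains cannot show the direction of lobular change in a patient unless L + B moves far enough; for falls, that means by at least 3 points.

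The conclusion rests on the SAP text as written. It says nothing about how often misleading patterns will occur. It is a worthwhile correction to secondary reporting.

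**What to change.** - In SAP 5.1.2.1 and 7.2.2, name the lobular inflammation component (0–3) as the direct measure of inflammation and add the ballooning component (0–2). Give baseline, Week 48 and change for each.
- Keep the prespecified total NAS summary, labelled as a composite activity score rather than as inflammation.
- Record the added rows and the relabelling, with the reason, in the SAP 4.2 change table.
- Summarise the METAVIR activity score required by protocol 8.1.1, or state in SAP 4.1 that it is omitted.
- Keep all of this descriptive; no hypothesis test is needed.

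The cost is a few words in the SAP and a few table rows. NAS cannot be computed without its components and METAVIR activity is already called for, so no new biopsy, reading or score is required.
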